1 PROTOCOL SUMMARY

[figure not shown]
1.1 SYNOPSIS

Title:	An exploratory study of the effect of bismuth subsalicylate on the gut microbiome and host response in healthy adults
Study Description:	This is a single-site, single-arm, open-label study to evaluate the effect of bismuth subsalicylate (BSS) on the human gut microbiome and host immune response. Upon confirmation of eligibility, healthy adult volunteers will provide stool and optional blood, saliva, urine, and intestinal biopsy samples for a baseline assessment of gut microbiome and host immune response. Up to 18 weeks later, participants will undergo a 2-day/8-dose regimen of oral BSS. Stool will be collected at baseline, days 2 (+3), 8 (± 3), 14 ($-3/+7$) and 28 (± 7). Blood, saliva, and urine are also optional at these time points. Participants may also undergo a second optional colonoscopy at day 8 (± 3) to provide colon biopsies for research analysis.
Primary Objective:	To evaluate the effect of BSS on the human gut microbiome.
Secondary Objective:	To evaluate the effect of BSS on the human gut metabolome.
Tertiary/Exploratory Objective:	To evaluate the effect of BSS on the systemic and intestinal host response (immune and inflammatory responses).
Primary Endpoint:	Differences in the relative abundance of taxa in stool samples pre-BSS and approximately 1 month post-BSS. Differences in microbiome metrics of alpha diversity and beta diversity will also be assessed.
Secondary Endpoint:	Differences in the stool metabolome (including short chain fatty acids, bile acids, and untargeted metabolomics) pre-BSS and approximately 1 month post-BSS.
Tertiary/Exploratory Endpoint:	Differences in systemic host immune and inflammatory responses, such as cytokines and immune cells, and host intestinal immune responses, such as specific T-cell populations in intestinal biopsies pre-BSS and approximately 1 month post-BSS.
Study Population:	Healthy adult volunteers aged 18 to 50 years, n=20, accrual ceiling 40.
Phase:	N/A
Description of Sites/Facilities	NIH Clinical Center (CC), Bethesda, MD
Enrolling Participants:	
Description of Study Intervention:	BSS oral suspension, self-administered at 4 doses of 1050 mg each per day (1 to 6 hours apart) for 2 days. This is within the recommended adult dose.
Study Duration:	3 years
Participant Duration:	Up to 22 weeks.

Abbreviated Title: BSS Gut Microbiome

Version Date: 05 July 2024

1.2 SCHEMA

Key

 Stool sample

 Blood draw (optional)

 Colonoscopy with biopsies and brushings (optional)

Abbreviated Title: BSS Gut Microbiome

Version Date: 05 July 2024

1.3 SCHEDULE OF ACTIVITIES

	Screening	Baseline	Intervention	Follow-up			
	Week -18 to -1	Week -18 to Week -1 ^a	Day 0	Day 2 (+3 days)	Day 8 (±3 days)	Day 14 (-3/+7 days)	Day 28 (±7 days)
Procedures	Remote	Remote or in-person	In-person	Remote or in-person	Remote or in-person	Remote or in-person	Remote or in-person
Informed consent	X ^b						
Physical exam			X				
Height			X				
Weight and vital signs			X				
Medical history and medication review	X ^c	X ^d	X	X	X	X	X
AE assessment			X	X	X	X	X
Provision of BSS			X				
Pregnancy test ^e		X ^f	X ^g		X ^h		
Stool collection		X ⁱ	X ⁱ	X	X ⁱ	X	X
Baseline questionnaire		X					
Survey (including diet)		X	X	X	X	X	X
Optional procedures							
Urine collection		X	X	X	X	X	X
Saliva collection		X	X	X	X	X	X
Colonoscopy with biopsies and brushings		X			X		
Chest X-ray		X ^j			X ^j		
GI consult		X ^k			X ^k		
Pre-anesthesia consult		X ^k			X ^j		
ECG		X ^j			X ^j		
Blood evaluations							
CBC/diff		X ^k			X ^j		
Acute care, hepatic, mineral panels		X ^k			X ^j		
PT/PTT/INR		X ^k			X ^j		
Platelet function assay		X ^k			X ^j		
Research blood draw ^l		X	X	X	X	X	X

	Screening	Baseline	Intervention	Follow-up			
	Week -18 to -1	Week -18 to Week -1 ^a	Day 0	Day 2 (+3 days)	Day 8 (±3 days)	Day 14 (-3/+7 days)	Day 28 (±7 days)
Procedures	Remote	Remote or in-person	In-person	Remote or in-person	Remote or in-person	Remote or in-person	Remote or in-person

AE, adverse event; BSS, bismuth subsalicylate; CBC/diff, complete blood count with differential; ECG, electrocardiogram; GI, gastrointestinal; PT/PTT/INR, prothrombin time, partial thromboplastin time, and international normalized ratio; X, to be performed.
 
a Baseline will be done after confirmation of eligibility. The overlap between the screening and baseline windows accounts for the required 30-day interval between the optional colonoscopies at baseline and day 8. Participants who do not undergo colonoscopy may have a shorter interval between screening, baseline, and day 0.
 
b The informed consent form will be signed before any research procedures are conducted on this study.
 
c Limited review of existing medical records may be done before the participant signs the informed consent form.
 
d Continued eligibility will be confirmed at the baseline visit.
 
e For participants of childbearing potential only. If the visit will be done remotely, then the participant will be instructed to send a urine sample to the study team, which will be used for pregnancy testing.
 
f For participants who will have the baseline colonoscopy, the timing of baseline pregnancy test will be per Department of Perioperative Medicine guidelines.
 
g To avoid repetition of procedures, pregnancy test will only be done at day 0 if baseline was more than 14 days before.
 
h Pregnancy test will only be done at day 8 if the participant will undergo the colonoscopy.
 
i Day 0 stool, which will be collected before first dose of BSS, may be collected up to 7 days earlier. For participants undergoing colonoscopy, stool samples will be attempted to be collected prior to the start of the bowel preparation.
 
j These procedures will only be done if the participant is undergoing the colonoscopy and the procedures are determined to be needed per the Department of Perioperative Medicine guidelines at the NIH Clinical Center. These labs will be repeated for the second (day 8) colonoscopy per the Department of Perioperative Medicine and if there are more than 30 days between it and the first procedure. For the convenience of the participant and study team, blood for the second colonoscopy may be drawn at the day 0 or 2 visits (the latter only if in person at the NIH Clinical Center).
 
k These procedures will only be done if the participant is undergoing the colonoscopy.
 
l Research blood draw is optional and will only be offered at in-person visits.
							

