3 OBJECTIVES AND ENDPOINTS

OBJECTIVES	ENDPOINTS	JUSTIFICATION FOR ENDPOINTS
Primary		
To evaluate the effect of BSS on the human gut microbiome.	Differences in the relative abundance of taxa in stool samples pre-BSS and approximately 1 month post-BSS. Differences in microbiome metrics of alpha diversity and beta diversity will also be assessed.	Hypothesis: there will be a decrease in beneficial bacterial taxa (eg, Lactobacillus) and increase in potential pathobionts (eg, Enterococcus). This will be most pronounced at day 2 (the day after therapy) and some changes may persist up to 1 month. This hypothesis is based on our findings in murine models (section 2.2.). These specific endpoints of relative abundance of taxa, alpha diversity, and beta diversity were chosen as they are standard metrics to assess changes in the microbiome.(28, 29)

OBJECTIVES	ENDPOINTS	JUSTIFICATION FOR ENDPOINTS
Secondary		
To evaluate the effect of BSS on the human gut metabolome.	Differences in the stool metabolome (including short chain fatty acids, bile acids, and untargeted metabolomics) pre-BSS and approximately 1 month post-BSS.	Hypothesis: there will be a change in specific stool metabolites (eg, a decrease in protective secondary bile acids and short chain fatty acids) with BSS therapy. This will correlate with gut microbiome changes. Stool metabolites are produced by gut microbiota and also contain host products. Importantly, they can assess the function of the microbiota, ie, “what are they doing” rather than just “what’s there.”(30) Moreover, bacterial metabolites have a key role in gut barrier function, host immunity, and inflammation, which is important in this study when assessing microbiome and host responses to BSS.(31) Targeted assays for metabolites of special interest, such as bile acids, short chain acids, and sulfides may be performed.(32, 33) Wide targeted or untargeted metabolite assays will also be performed to uncover other metabolites of relevance.
Tertiary/Exploratory		

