4 STUDY DESIGN

4.1 OVERALL DESIGN

This is an exploratory, single-site, single-arm, open-label study of the effects of BSS on the human gut microbiome and host response. It is hypothesized that there will be a decrease in

beneficial bacterial taxa (eg, *Lactobacillus*) and increase in potential pathobionts (eg, *Enterococcus*) as seen in murine models (section 2.2).

Upon confirmation of eligibility, healthy adult volunteers (n=20) will undergo baseline assessment of gut microbiome and host response by providing a stool sample. Participants also have the option to provide blood, urine, and saliva, and to undergo colonoscopy for collection of biopsies and brushings. Approximately 1 to 18 weeks later, they will provide another stool sample (with optional blood, urine, and saliva), and then begin a brief regimen of BSS: 1050 mg 4 times daily (about 1 to 6 hours apart) for 2 days. Remote or in-person follow-up visits will be at days 2 (+3), 8 (± 3), 14 ($-3/+7$), and 28 (± 7). Participants will be assessed for AEs and provide stool samples, and have the option to provide blood, urine, and saliva. Participants may also have a second colonoscopy with collection of biopsies and brushings at the day 8 follow-up visit.

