5.2 EXCLUSION CRITERIA

An individual who meets any of the following criteria will be excluded from participation in this study:

1. Use of systemic antibiotics in the last 3 months.
2. BSS use in the last 3 months.
3. Pregnant or breastfeeding.
4. Allergy to BSS.
5. Allergy to other salicylates (including aspirin).
6. Current use of other salicylates (including aspirin).
7. Current use of anticoagulant medications.
8. History of or active GI ulcers.
9. History of or active bleeding disorder.
10. Bloody stool within the last 3 months.
11. Diarrhea within the last 2 weeks (defined as three or more loose or liquid stools per day).
12. Current use of medications that may have a drug interaction with BSS (section 6.4).
13. Not proficient in written English.
14. Currently participating in another clinical trial that may affect current study procedures, per investigator's discretion.
15. Any condition that, in the opinion of the study team, contraindicates participation in this study.

Co-enrollment in other studies is restricted. Consideration for co-enrollment in clinical trials evaluating the use of a licensed medication will require the approval of the principal investigator. Study staff should be notified of co-enrollment on any other protocol as it may require the approval of the principal investigator.

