8.2 STUDY EVALUATIONS & PROCEDURES

Targeted physical exam: The components of the exam will be at the discretion of the investigator. Weight and vital signs will be measured.

Baseline questionnaire: This will include questions regarding demographics, medical history, and medications. Participants may complete this questionnaire on paper or electronically via REDCap system.

Survey: A brief survey containing questions regarding diet and other factors that can affect the gut microbiome will be administered at each visit. Participants may complete this questionnaire on paper or electronically via REDCap.

Colonoscopy: Colonoscopy is an optional procedure for collection of intestinal biopsies and brushings. This procedure will be limited to those 30 years of age or younger. This is because the chance of incidental findings such as intestinal polyps are lower at this age.⁽³⁹⁾ If an incidental polyp was found, a polypectomy may need to be carried out at the discretion of the gastroenterologist performing the procedure, and this increases the risk of a colonoscopy.

Up to 20 research biopsies may be obtained from the colon and ileum. If a participant agrees to this procedure, then they will undergo it at baseline and the day 8 visit. Baseline has a window between weeks -18 and -1, so it will be scheduled relative to day 0 so there are at least 30 days between colonoscopy procedures. Colonoscopy preparation will be per standard process, and participants will be instructed accordingly. Before the first procedure to ensure participant safety,

participants will have a GI consultation, a pre-anesthesia consultation, clinical blood evaluations (section 8.2.1), and a pregnancy test (if of childbearing potential); an ECG and chest X-ray may be conducted if they are determined to be needed per the Department of Perioperative Medicine guidelines at the NIH CC. These procedures, except the pregnancy test, will only be repeated up to 8 days before the second procedure if there are more than 30 days between colonoscopies and if they are determined to be needed per the Department of Perioperative Medicine guidelines at the NIH CC. A pregnancy test will always be done before both colonoscopies for participants who can get pregnant. Biopsies and brushings will be collected for research purposes, as described in section 8.2.1.

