9.4.5 Sub-Group Analyses

Subgroup analysis is not warranted given the small sample size of this study.

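### The 1-month primary contrast pools stools taken after the day 8 bowel preparation, or after interim antibiotics, with unaffected stools, and section 9 has no analysis that sets them apart

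*Combined protocol and SAP*

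**What the plan says.** Section 3 sets the primary endpoint as "Differences in the relative abundance of taxa in stool samples pre-BSS and approximately 1 month post-BSS". Section 9.2 names a paired t-test on the log10 change at each post-treatment time point. Section 9.4.2 adds linear discriminant analysis effect size and alpha and beta diversity, again comparing each time point with pre-treatment. Section 9.3 includes everyone with a baseline stool and at least one stool after BSS. The trial has a single arm.

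On colonoscopy, section 8.2 limits the optional procedure to age 30 or younger and says "If a participant agrees to this procedure, then they will undergo it at baseline and the day 8 visit". On spacing it adds "so it will be scheduled relative to day 0 so there are at least 30 days between colonoscopy procedures". On stool timing, footnote i of section 1.3 says "For participants undergoing colonoscopy, stool samples will be attempted to be collected prior to the start of the bowel preparation". That footnote is attached to the baseline, day 0 and day 8 stools, not to the day 14 or day 28 stools.

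On other influences, section 5.2 excludes "Use of systemic antibiotics in the last 3 months". Footnote d of section 1.3 says "Continued eligibility will be confirmed at the baseline visit", and the baseline visit may be as early as week -18. Section 6.4 names tetracyclines as the only antibacterial class prohibited during the study, because of a drug interaction. It also advises participants to avoid non-study BSS. Medication review and a survey are scheduled at day 0 and at each follow-up visit. Section 9 does not say how that information enters the analysis. Section 9.4.5 says "Subgroup analysis is not warranted given the small sample size of this study".

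**The concern.** Footnote i shows that the plan regards stool taken after bowel preparation as different from stool taken before it. The safeguard covers the visit at which the colonoscopy takes place. It cannot cover the visits that follow, and the primary endpoint is read at the last of them. A colonoscopy participant's change from pre-BSS to day 28 therefore spans a course of BSS and, about a week later, a bowel preparation. With no control arm and no term, exclusion or sensitivity analysis for preparation, a lasting shift from it would be counted as BSS.

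Antibiotics raise the same problem. Section 2.2.4 sets aside earlier studies of BSS given with antibiotics because the antibiotic effect probably prevents interpretation. Yet section 9 is silent on samples taken after a participant receives a systemic antibiotic between baseline and day 28.

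What is at stake is the persistence claim. Section 9.1 expects the effect to be largest at day 2, with only some changes lasting to 1 month. A small expected day 28 signal is the kind most easily imitated or hidden by another influence.

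**Working it through.** **The plan's own figure.** The documents give no number for this issue. The only figure tied to the primary endpoint is Table 1 in section 9.2, with 87% power for a 2-log10 change at N = 20 and SD 2. A two-sample t-test with 20 per group (two-sided 5%) gives 86.9% and matches the whole table to within 2 points. The paired t-test named in the text, with 2 as the SD of the change, gives 98.9%. Power is therefore shown on both bases below.

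**Timing after the second colonoscopy** (windows from sections 1.3 and 4.1)
- Day 8 (±3): days 5 to 11.
- Day 14 (-3/+7): days 11 to 21. Gap: 11 - 11 = 0 to 21 - 5 = 16 days.
- Day 28 (±7): days 21 to 35. Gap: 21 - 11 = 10 to 35 - 5 = 30 days.

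Preparation precedes the procedure, so the gap from preparation is slightly longer. The day 8 and day 14 windows touch only on day 11. The day 28 stool always follows preparation.

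**Timing around the first colonoscopy.** With at least 30 days between procedures, the first falls no later than 5 - 30 = day -25 to 11 - 30 = day -19. The day 0 stool may be taken up to 7 days early, on day -7. The shortest gap is -7 - (-19) = 12 days. The day 0 stool of a colonoscopy participant thus also follows a preparation, while the baseline-visit stool precedes both if the attempt succeeds. The plan does not say which of the two is the pre-BSS reference.

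**Eligibility.** 18 weeks × 7 = 126 days, which exceeds 3 months. The whole antibiotic look-back period before day 0 can therefore fall after the last stated eligibility confirmation.

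**Size of a possible bias.** Let k of 20 participants carry a residual day 28 shift of b log10, and suppose BSS has no effect. Both k and b are assumptions. With an unaffected reference stool:

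bias in mean change = (k/20) × b

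If the day 0 stool is the reference and has its own residual b0, this becomes (k/20) × (b - b0). The table gives simulated rejection rates of the nominal 5% paired t-test at n = 20 with an unaffected reference. SD is that of the individual change apart from the shift.

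| k | b | bias (log10) | SD 0.5 | SD 1 | SD 2 | SD 3 |
|---|---|---|---|---|---|---|
| 0 | any | 0 | 5% | 5% | 5% | 5% |
| 5 | 0.5 | 0.125 | 14% | 8% | 6% | 5% |
| 5 | 1.0 | 0.25 | 31% | 14% | 8% | 6% |
| 10 | 0.5 | 0.25 | 47% | 17% | 8% | 6% |
| 10 | 1.0 | 0.50 | 92% | 47% | 17% | 10% |

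**Cost of setting samples aside.** The standard error grows by √(20/m) when m participants remain.
- m = 15: √(20/15) = 1.15, about 15% larger. Power for 2 log10 at SD 2 is 94.9% (paired) or 75.3% (Table 1 basis).
- m = 10: √(20/10) = 1.41, about 41% larger. Power is 80.3% (paired) or 56.2% (Table 1 basis).

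**The case against.** The strongest reply is that the harm is hypothetical. Colonoscopy is optional and limited to age 30 or younger in a trial that enrols to age 50. The documents give neither an expected uptake nor any preparation effect lasting 10 to 30 days. Footnote i shows concern about same-visit stool only. At the plan's headline SD of 2 the distortion is small unless both k and b are large. The trial is an exploratory pilot meant to precede a randomized study, and the day 2 stool, where the effect is expected to peak, comes before the second preparation. If day 0 is the reference, similar residual shifts at day 0 and day 28 would partly cancel. All of this stands, and it limits the point to a risk of unknown size.

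Two stronger readings are not supported. A reader might infer that preparation and BSS are completely confounded at day 28. That is so only within colonoscopy participants. The others give day 28 stools with no preparation behind them, so the effects can be separated across participants if the plan provides for it. A reader might also infer that the affected samples cannot be identified, or that section 9.4.5 forbids separating them. But colonoscopy is a scheduled study procedure, medications are recorded at each visit, and a sensitivity analysis that drops samples is not a subgroup analysis.

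The reply does not supply any stated handling. The data are collected, but the 1-month analysis as written makes no use of them.

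**Conclusion.** The point holds as a gap in the analysis plan. The timing follows from the protocol's own windows and needs no outside assumption: every in-window day 28 stool from a colonoscopy participant follows the second bowel preparation, and the plan pools it without distinction. The size of any bias does not follow from the documents. It runs from zero (no colonoscopies, or no lasting effect) through rejection rates of about 6 to 8% (k = 5, b = 0.5, SD 2 to SD 1) and 8 to 17% (k = 10, b = 0.5) to much larger values if k and b are both high or the SD is low. No magnitude can be given for interim antibiotics.

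That post-antibiotic samples would be kept is inferred from section 9.3, which sets no such exclusion. As written, a day 28 difference could not be attributed to BSS without an analysis chosen after seeing the data.

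**What to change.** 1. Keep the stated paired analysis as primary. In section 9.4.2, prespecify a sensitivity analysis of the day 14 and day 28 contrasts that excludes samples taken after the day 8 bowel preparation, after interim systemic antibiotics, or after non-study BSS.
2. State that section 9.4.5 does not bar this analysis.
3. Name which pre-BSS stool, baseline visit or day 0, is the reference.
4. State that existing exclusion criteria 1, 2 and 11 are checked again at day 0, using the medication review already scheduled there.
5. If the baseline-to-day-0 change is shown by colonoscopy status, label it descriptive. The groups differ in age and possibly in interval, so it is not a clean estimate of the preparation effect.

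The cost is protocol wording and one added check at day 0, with no new samples or visits. The statistical cost is a less precise day 28 estimate in the sensitivity analysis only, with a standard error about 15% larger if 5 of 20 are set aside and about 41% larger if 10 are.

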
2 INTRODUCTION

2.1 STUDY RATIONALE

BSS is a commonly used, widely available, over-the-counter (OTC) medication for a variety of gastrointestinal (GI) symptoms. Side effects are generally rare and short-lived. Our laboratory has recently shown in murine models that BSS, in doses scaled down to mice from recommended adult dosing, has a profound effect on the gut microbiome, with a depletion of *Lactobacillus* and increase in *Enterococcus*. This treatment also impacted the host immune response, including a decrease in CD4+ T cells in the small intestine. These mice were more susceptible to the pathogenic effects of a subsequent *Salmonella* infection (unpublished data, manuscript in preparation). The effect of BSS alone on the human gut microbiome has not previously been investigated. Given our recent findings in murine models and the known critical role of the host-microbiome response in human health and disease, this is an important area to study in humans as BSS is commonly used. Therefore, we propose to assess whether the effect of BSS seen on the gut microbiome and host response in murine models is also seen in healthy human volunteers. If an effect is seen, this lays the foundation for further studies to assess the clinical impact and potential health outcomes of these changes in humans.

